9. BIOMARKER, CORRELATIVE, AND SPECIAL STUDIES

Specimens will be collected for several planned correlative studies. Many samples will be processed and stored to be run in batches. The CITN Immune Monitoring Laboratory will provide lab kits and shipping supplies. Specific instructions on numbers and types of tubes required for each visit are provided in the CITN-14 Laboratory Manual.

When blood volume or specimen material is limited, the correlative studies will be considered secondary to tests needed to make clinical decisions. Prioritization of secondary tests will be made based on technical considerations, total amount of sample from each individual subject, total number of samples acquired, total number of each assay performed, and information gained from the assays performed to date. The anticipated priority correlatives are:

Plasma/serum-based studies

1. Multiplex Cytokines – Multiplex ELISA
2. Kynurenine and tryptophan (Kyn/Trp) ratios and

Cell associated studies

1. Evaluation of peripheral CD4+ and CD8+ T-cell counts
2. T-Cell Receptor Repertoire Analysis – TCR sequencing
3. Evaluation of the effect of atezolizumab with and without CYT107 on circulating Lymphocyte and Monocyte numbers and Phenotype
4. Tumor-Associated Neoantigen discovery – Whole Exome Sequencing and RNAseq and Antigen Prediction
5. Antitumor Immune T-cell Responses

Biopsy associated studies

1. Slide-Based Immune Phenotype Panel – Multispectral IHC
2. Assessment of tumor biopsy by gene expression analysis -- Interferon γ (INF γ) Gene Expression Signature - NanoString[®] nCounter[®] Human Immunology V2 Panel and the nCounter[®] PanCancer Immune Profiling Panel

3. Assessment of PD-L1 expression at Baseline and Post-treatment – Immunohistochemistry (IHC)
4. Tumor-Associated Neoantigen discovery – Whole Exome Sequencing and RNAseq and Antigen Prediction

9.1 Integrated Correlative Studies

9.1.1 Evaluation of peripheral CD4+ and CD8+ T-cell counts – Integrated Laboratory Correlative Study #1

9.1.1.1 *Collection of Specimen(s)*

Blood draws will be performed by venipuncture on study subjects in Red-Top or Gold SST or other blood draw tubes as specified per local site SOP.

9.1.1.2 *Handling of Specimens(s)*

Blood Samples will be collected at room temperature and shipped ambient to the local clinical lab.

9.1.1.3 *Shipping of Specimen(s)*

Blood collection tubes will be shipped at ambient temperature to the designated local clinical, CLIA compliant laboratory the same day as the blood draw.

9.1.1.4 *Site(s) Performing Correlative Study*

Assays will be performed at each local clinical site. Assays are to be performed at each site by a CLIA compliant laboratory. The specific technique is not specified in the protocol.

9.1.2 Slide-Based Immune Phenotype Panel – Multispectral IHC – Integrated Laboratory Correlative Study #2

9.1.2.1 *Collection of Specimen(s)*

Formalin-fixed, paraffin-embedded archival tissue block(s) from tumor obtained within 2 years from the screening visit will be identified by the clinical site at the relevant pathology laboratories where they were processed and stored. Tissue blocks are preferred, however FFPE slides can substitute if blocks are unavailable. Alternatively, patients will undergo a pre-treatment biopsy (core, punch, or excisional) as part of this protocol. Patient will undergo a post-treatment biopsy (core, punch, or excisional) if deemed relatively safe and technically feasible as part of this protocol.

9.1.2.2 *Handling of Specimens(s)*

Formalin-fixed, paraffin-embedded archival tumor blocks will be requested by fax and phone by the clinical site from the relevant pathology laboratory by providing the patient's name, consent form, and date of collection. If patients undergo biopsy as part of this protocol, tissue will be placed in formalin for overnight shipping to the CIML.

9.1.2.3 *Shipping of Specimen(s)*

For archival samples, clinical sites will arrange for the formalin-fixed, paraffin-embedded tumor blocks or FFPE slide to be shipped at ambient temperature to the CIML. For biopsies done as part of this protocol, tissue in formalin will be shipped overnight at ambient temperature to the CIML. Clinical sites will utilize a web-based specimen system (BSI-Web) to communicate with the CIML. After sectioning at the CIML, the CIML will coordinate shipment of unstained slides to Dr. [REDACTED] at Fred Hutch.

9.1.2.4 *Site(s) Performing Correlative Study*

Assays will be performed by Dr. [REDACTED] at Fred Hutch.

9.1.3 *Assessment of tumor biopsy by gene expression analysis -- Interferon γ (INF γ) Gene Expression Signature - NanoString[®] nCounter[®] Human Immunology V2 Panel and the nCounter[®] PanCancer Immune Profiling Panel – Integrated Laboratory Correlative Study #3*

9.1.3.1 *Collection of Specimen(s)*

Formalin-fixed, paraffin-embedded archival tissue block(s) from tumor obtained within 2 years from the screening visit will be identified by the clinical site at the relevant pathology laboratories where they were processed and stored. Alternatively, patients will undergo a pre-treatment biopsy (core, punch, or excisional) as part of this protocol. Patients will undergo a post-treatment biopsy (core, punch, or excisional) if deemed relatively safe and technically feasible as part of this protocol.

9.1.3.2 *Handling of Specimens(s)*

Formalin-fixed, paraffin-embedded archival tumor blocks will be requested by fax and phone by the clinical site from the relevant pathology laboratory by providing the patient's name, consent form, and date of collection. If patients undergo biopsy as part of this protocol, tissue will be placed in formalin for overnight shipping to the CIML.

9.1.3.3 *Shipping of Specimen(s)*

For archival samples, clinical sites will arrange for the formalin-fixed, paraffin-embedded tumor blocks (preferred) or FFPE slides (if blocks are unavailable) to be shipped at ambient temperature to the CIML. For biopsies done as part of this protocol, tissue in formalin will be shipped overnight at ambient temperature to the CIML. Clinical sites will utilize a web-based specimen system (BSI-Web) to communicate with the CIML. After sectioning at the CIML, the CIML will coordinate shipment of unstained slides (or RNA) to NanoString[®]. Depending on the specific contract, RNA will be extracted from FFPE slides, either at NanoString[®] or the CIML, using established protocols (MAN-10050-02 Preparing Nucleic Acid from FFPE Samples for Use with nCounter[®] Assays).

9.1.3.4 *Site(s) Performing Correlative Study*

Assays will be performed by NanoString® Technologies in Seattle, WA, and analyzed using qualified analytic tools at the immunopathology lab of Fred Hutch.

9.1.4 *T-Cell Receptor Repertoire Analysis – TCR sequencing – Integrated Laboratory Correlative Study #4*

9.1.4.1 *Collection of Specimen(s)*

Specimens will include archived and prospectively obtained tumor biopsies and blood samples. Blood draws will be performed by venipuncture.

9.1.4.2 *Handling of Specimens(s)*

Biopsy samples will be placed in formalin and shipped to the CIML. Blood collection tubes will be shipped on day of blood draw for overnight delivery to the CIML.

9.1.4.3 *Shipping of Specimen(s)*

Whole blood and biopsies in formalin will be shipped ambient to the CIML. Blood will be processed to PBMC as described above. Clinical sites will utilize a web-based specimen system (BSI-Web) to communicate with the CIML. The CIML will coordinate shipment of samples to Adaptive Biosciences.

9.1.4.4 *Site(s) Performing Correlative Study*

Samples will be analyzed at Adaptive Bioscience in Seattle, WA, or other agreed upon vendor or collaborator.

9.1.5 *Tumor-Associated Neoantigen discovery – Whole Exome Sequencing and RNAseq and Antigen Prediction – Integrated Laboratory Correlative Study #5*

9.1.5.1 *Collection of Specimen(s)*

Specimens will include archived tumor blocks (or FFPE slides) and prospectively obtained tumor biopsies and blood samples. Blood draws will be performed by venipuncture.

9.1.5.2 *Handling of Specimens(s)*

For archival samples, clinical sites will arrange for the formalin-fixed, paraffin embedded tumor specimens to be shipped at ambient temperature to the CIML. For biopsies done as part of this protocol, tissue in formalin will be shipped overnight at ambient temperature to the CIML where they will be embedded in paraffin. Paraffin blocks (or FFPE slides) will be stored at 4°C under desiccant.

Blood collection tubes will be shipped on day of blood draw for overnight delivery to the CIML. Blood will be processed to PBMC as described above and stored in liquid nitrogen. Nucleic acid will be extracted from PBMC and from biopsy specimens using vendor-specific protocols.

9.1.5.3 *Shipping of Specimen(s)*

Whole blood, archival tumor blocks (or FFPE slides) and biopsies in formalin will be shipped ambient to the CIML. Clinical sites will utilize a web-based specimen system (BSI-Web) to communicate with the CIML. The CIML will coordinate shipment of samples to the Fred Hutch immunopathology lab and/or agreed upon vendor.

9.1.5.4 *Site(s) Performing Correlative Study*

These analyses will be performed using qualified analytes and analytic tools at the immunopathology lab and shared resources of the Fred Hutch or at a vendor to be determined.

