2.5 Integrated Correlative Studies Background

2.5.1 Evaluation of peripheral CD4+ and CD8+ T-cell counts – Integrated Laboratory Correlative Study #1

As described above, CYT107 has been shown to double the number of peripheral blood lymphocytes including T cells. Thus, CD4+ and CD8+ T-cell numbers are important biomarkers for the effect of CYT107 on the peripheral T-cell populations. To assess the overall pharmacodynamic effect of atezolizumab plus CYT107 and to determine whether CYT107 in combination with atezolizumab results in the same, or different level, of expansion of peripheral lymphocytes, T-cell counts (both CD4+ and CD8+) will be evaluated in CLIA certified laboratories locally at each site. CD4+ and CD8+ T-cell counts will be evaluated at baseline, during treatment, and at end of therapy.

Hypothesis: The combination of atezolizumab with CYT107 will result in similar levels of peripheral blood T-cell expansion as with CYT107 alone.

2.5.2 Slide-Based Immune Phenotype Panel -- Multispectral IHC – Integrated Laboratory Correlative Study #2

Because tumor-infiltrating immune cells are associated with clinical outcomes, infiltrates from pre-treatment tumor tissue and from biopsies taken during treatment will be assessed by IHC to determine extent and the nature of T-cell infiltration and of the overall immune milieu of the tumor microenvironment (TME).

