Blood Samples will be collected at room temperature and shipped ambient to the CIML the same day as the blood draw. The sample must be received at the CIML within 24 hours of blood draw.

9.2.2.3 *Shipping of Specimen(s)*

Blood collection tubes will be shipped at ambient temperature to the CIML. Clinical sites will utilize a web-based specimen system (BSI-Web) to communicate with the CIML.

9.2.2.4 *Site(s) Performing Correlative Study*

Quantification of PBMC and T-cell subsets will be performed under the direction of Dr. [REDACTED] in the CIML at Fred Hutch.

9.2.3 *Multiplex Cytokines -- Multiplex ELISA – Exploratory Laboratory Correlative Study #3*

9.2.3.1 *Collection of Specimen(s)*

Whole blood will be collected into red-top tubes by venipuncture.

9.2.3.2 *Handling of Specimens(s)*

Blood samples will be processed to frozen serum at the local labs and stored frozen at -80°C.

9.2.3.3 *Shipping of Specimen(s)*

Frozen serum vials will be shipped from clinical sites to the CIML. Clinical sites will utilize a web-based specimen system (BSI-Web) to communicate with the CIML. The CIML will coordinate shipments of serum to the Fred Hutch Shared Resource facility or other collaborator, as needed.

9.2.3.4 *Site(s) Performing Correlative Study*

Assays will be performed at the Fred Hutch Shared Resource facility or other agreed upon collaborator or vendor.

9.2.4 *Kynurenine and tryptophan (Kyn/Trp) Ratios and Plasma Arginine levels – Exploratory Laboratory Correlative Study #4*

9.2.4.1 *Collection of Specimen(s)*

Blood draws will be performed by venipuncture on study subjects at time points before, during, and after treatment.

9.2.4.2 *Handling of Specimens(s)*

Plasma will be isolated by the local laboratory and frozen at -80°C.

9.2.4.3 *Shipping of Specimen(s)*

Plasma samples will be batch shipped overnight on dry ice to the CIML. Sites will utilize a web-based specimen system (BSI-Web) to communicate with the CIML. The CIML will coordinate the shipment of samples to the agreed upon collaborator or vendor.

9.2.4.4 *Site(s) Performing Correlative Study*

Kynurenine and tryptophan and Arginine levels will be assessed at an agreed upon collaborator or vendor to be determined.

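### Section 9.1.1.1 names two serum tubes, Red-Top and Gold SST, for the local CD4+/CD8+ T-cell counts; neither can give a cell count, so only the local-SOP fallback yields a usable sample

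*Combined protocol and SAP*

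**What the plan says.** Section 2.5.1 sets up Integrated Correlative Study #1 and states that "T-cell counts (both CD4+ and CD8+) will be evaluated in CLIA certified laboratories locally at each site". It gives the reason: "CD4+ and CD8+ T-cell numbers are important biomarkers for the effect of CYT107 on the peripheral T-cell populations". The priority list at the start of Section 9 puts "Evaluation of peripheral CD4+ and CD8+ T-cell counts" first among the cell-associated studies, in a different group from the plasma and serum studies.

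Section 9.1.1.1 says the blood is taken by venipuncture "on study subjects in Red-Top or Gold SST or other blood draw tubes as specified per local site SOP". Sections 9.1.1.2 and 9.1.1.3 send it at ambient temperature to the local laboratory on the day of the draw and mention no anticoagulant. Section 9.1.1.4 adds: "The specific technique is not specified in the protocol".

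The red-top tube appears again in Section 9.2.3, for the multiplex cytokine assay. There, "Whole blood will be collected into red-top tubes by venipuncture", and then "Blood samples will be processed to frozen serum at the local labs".

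Two other places bear on the point. Section 2.6.2 describes a separate central whole-blood flow cytometry panel that reports absolute CD4+ and CD8+ T-cell numbers. The opening of Section 9 refers to a Laboratory Manual for the tubes needed at each visit; that manual is not among the documents.

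**The concern.** A lymphocyte subset count needs intact cells in unclotted blood. In a serum tube the blood clots, the cells are held in the clot, and the fluid that remains contains none to count. Section 9.1.1.1 puts two such tubes at the head of its list. The third option, any other tube under the local SOP, is the only one that can work, and it carries no requirement for an anticoagulant. A site that follows the sentence literally and picks a named tube complies with the protocol and obtains no result.

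What is at stake is part of the pharmacodynamic record. The rationale in Section 2.4 is that CYT107 expands the T-cell pool, and these counts are the most frequent measurement of that expansion. A sample meant to be taken before a given dose cannot be recovered later.

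**Working it through.** No power or alpha figure is involved. The check has two parts: whether the named tubes fit the assay, and how many scheduled counts have no other source.

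**1. Tube against assay**

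- Section 9 treats the counts as a cell-associated study, so the specimen must contain cells.
- Section 9.2.3 shows what a red-top tube yields in this protocol: serum.
- SST is the usual abbreviation for a serum separator tube, so Gold SST belongs to the same class.
- Section 2.6.2 counts the same CD4+ and CD8+ cells in whole blood.

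The documents do not themselves say that clotting makes a cell count impossible. That step is general laboratory knowledge. The mismatch between a cell-associated study and serum tubes is visible in the text.

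**2. Scheduled counts and their backup**

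Inputs: 48 randomized patients at 1:1, so 48 / 2 = 24 per arm, and 6 run-in patients (Section 13.3). Visits come from the two Section 10 calendars. Their footnotes call for T-cell counts before atezolizumab doses 1 to 4 and dose 6; the experimental calendar adds Weeks 1, 3 and 4.

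| | Local count scheduled | Central immunophenotyping at the same visit | No same-visit backup |
|---|---|---|---|
| Experimental arm and run-in | Weeks 1, 2, 3, 4, 5, 8, 11, pre-dose 6 (8) | Weeks 1, 2, 5, 8 (4) | Weeks 3, 4, 11, pre-dose 6 (4) |
| Control arm | Weeks 1, 4, 7, 10, pre-dose 6 (5) | Weeks 1, 4, 7 (3) | Week 10, pre-dose 6 (2) |

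Randomized part:

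- Scheduled: 24×8 + 24×5 = 192 + 120 = 312
- With backup: 24×4 + 24×3 = 96 + 72 = 168
- Without backup: 24×4 + 24×2 = 96 + 48 = 144, and 168 + 144 = 312
- Share without backup: 144 / 312 = 46%

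Run-in:

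- Scheduled: 6×8 = 48
- Without backup: 6×4 = 24, or 50%

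These are maxima. They assume that every patient reaches the sixth atezolizumab dose, and they count six run-in patients with no replacements.

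Section 2.5.1 also mentions a count at the end of therapy, which neither calendar marks in the T-cell row. Immunophenotyping is marked at that visit, so adding it would leave the 144 and the 24 unchanged.

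**3. Which visits are exposed**

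Weeks 3 and 4 in the experimental arm are the visits of the third and fourth CYT107 doses, with blood taken before dosing. They show how expansion builds during the course. Week 5, one week after the fourth dose, has a central count, and so does Week 1, the baseline.

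**The case against.** The strongest reply is that the sentence mandates neither tube. It permits any other tube under the local SOP, and the assay is run by a CLIA laboratory that would probably insist on its own validated specimen (an assumption, but a reasonable one). The Laboratory Manual may also name a correct tube. This stands to the extent that a reader who infers that Study #1 as a whole cannot be measured goes beyond the text. It does not rescue the two names. The fallback asks for no anticoagulant, and a correct manual would then disagree with the protocol. The manual may not cover these samples at all, since its kits come from the central laboratory and these counts are run locally.

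A second reply is that the central panel already measures the same cells in both arms. That also stands, and it removes much of the consequence: just over half of the randomized time points (168 of 312) have a same-visit central count. The CBC with differential, drawn at every Week-numbered count visit, gives total lymphocytes as well, though not the CD4+/CD8+ split.

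A third reply is that nothing inferential rests on these counts. Section 13 gives no test, power or decision rule for peripheral CD4+/CD8+ numbers; its only powered correlative uses paired biopsies. This is correct and keeps the point minor.

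Finally, one might want the protocol to require flow cytometry for Study #1. Section 9.1.1.4 leaves technique to the local laboratories by an explicit choice, and that choice is not an error.

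**Conclusion.** The point holds in a limited form. Both tubes named in Section 9.1.1.1 are wrong for a cell count, and a sample drawn in either gives no local result. The counts with no same-visit alternative are experimental Weeks 3, 4, 11 and pre-dose 6, and control Week 10 and pre-dose 6: at most 144 of 312 randomized samples and 24 of 48 run-in samples.

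Two stronger inferences are not supported. The first is that a negative ORR result could not be interpreted, because the trial could not tell a failure to expand T cells from expansion without benefit. The central counts at baseline, Week 2, Week 5 and Week 8 would still show whether expansion occurred; what could be lost is detail within the course and later on. The second is that 312 + 48 samples stand to be lost. That is every scheduled sample. The number actually drawn in a named tube cannot be estimated from the documents and may be zero.

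ORR and the sample size do not depend on these counts. Safety is also unaffected: the lymphocyte rule in Section 6.2 uses the total lymphocyte count, for which the calendar has its own CBC with differential.

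The conclusion rests on the general laboratory fact that clotted blood cannot be counted, and on the calendars as read. Severity is minor; the text is wrong as written.

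**What to change.** In Section 9.1.1.1, delete Red-Top and Gold SST, and require an anticoagulated whole-blood tube that the local CLIA laboratory accepts for lymphocyte subset counts. Leave the choice of technique in Section 9.1.1.4 as it is. Check that the Laboratory Manual agrees with the amended sentence, or states that it does not cover these local samples.

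The cost is one sentence in the protocol and one check of the manual. No visit or venipuncture is added, because the draw is already scheduled and only the tube changes.

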9.1.6 Antitumor Immune T-cell Responses -- ELISPOT – Integrated Laboratory Correlative Study #6

9.1.6.1 *Collection of Specimen(s)*

Blood draws will be performed by venipuncture on study subjects just before, during, and at end of treatment.

9.1.6.2 *Handling of Specimens(s)*

Blood collection tubes (for subsequent PBMC isolation) will be shipped on day of blood draw for overnight delivery to the CIML.

9.1.6.3 *Shipping of Specimen(s)*

Blood collection tubes will be shipped overnight at ambient temperature to the CIML using CIML established SOPs. Clinical sites will utilize a web-based specimen system (BSI-Web) to communicate with the CIML. The CIML will coordinate shipment via cryoport of cryopreserved PBMC in the event that a vendor or collaborator performs these studies.

9.1.6.4 *Site(s) Performing Correlative Study*

Assays will be performed in the CIML at Fred Hutch under the direction of Dr. [REDACTED] or an agreed upon vendor or collaborator.

9.2 Exploratory Correlative Studies

9.2.1 Assessment of PD-L1 expression at Baseline and Post-treatment -- Immunohistochemistry (IHC) – Exploratory Laboratory Correlative Study #1

9.2.1.1 *Collection of Specimen(s)*

Formalin-fixed, paraffin-embedded archival tissue block(s) from tumor obtained within 2 years from the screening visit will be identified by the clinical site at the relevant pathology laboratories where they were processed and stored. Tissue blocks are preferred, however FFPE slides can substitute if blocks are unavailable.

Alternatively, patients will undergo a pre-treatment biopsy (core, punch, or excisional) as part of this protocol. Patients will undergo a post-treatment biopsy

(core, punch, or excisional) if deemed relatively safe and technically feasible as part of this protocol.

9.2.1.2 *Handling of Specimens(s)*

Formalin-fixed, paraffin-embedded archival tumor blocks will be requested by fax and phone by the clinical site from the relevant pathology laboratory by providing the patient's name, consent form, and date of collection. If patients undergo biopsy as part of this protocol, tissue will be placed in formalin for overnight shipping to the CIML.

9.2.1.3 *Shipping of Specimen(s)*

For archival samples, clinical sites will arrange for the formalin-fixed, paraffin-embedded tumor blocks (preferred) or FFPE slides (if blocks are unavailable) to be shipped at ambient temperature to the CIML. For biopsies done as part of this protocol, tissue in formalin will be shipped overnight at ambient temperature to the CIML. Clinical sites will utilize a web-based specimen system (BSI-Web) to communicate with the CIML. After sectioning at the CIML, the CIML will coordinate shipment of unstained slides to HistoGeneX (Naperville, IL) or other agreed upon vendor.

9.2.1.4 *Site(s) Performing Correlative Study*

Assays will be performed by HistoGeneX or other agreed upon vendor. Samples would be run in batches.

9.2.2 *Evaluation of the effect of atezolizumab with and without CYT107 on circulating Lymphocyte and Monocyte numbers and Phenotype – Exploratory Laboratory Correlative Study #2*

9.2.2.1 *Collection of Specimen(s)*

Blood draws will be performed by venipuncture on study subjects just before, during, and at end of treatment.

9.2.2.2 *Handling of Specimens(s)*

Blood Samples will be collected at room temperature and shipped ambient to the CIML the same day as the blood draw. The sample must be received at the CIML within 24 hours of blood draw.

9.2.2.3 *Shipping of Specimen(s)*

Blood collection tubes will be shipped at ambient temperature to the CIML. Clinical sites will utilize a web-based specimen system (BSI-Web) to communicate with the CIML.

9.2.2.4 *Site(s) Performing Correlative Study*

Quantification of PBMC and T-cell subsets will be performed under the direction of Dr. [REDACTED] in the CIML at Fred Hutch.

9.2.3 *Multiplex Cytokines -- Multiplex ELISA – Exploratory Laboratory Correlative Study #3*

9.2.3.1 *Collection of Specimen(s)*

Whole blood will be collected into red-top tubes by venipuncture.

9.2.3.2 *Handling of Specimens(s)*

Blood samples will be processed to frozen serum at the local labs and stored frozen at -80°C.

9.2.3.3 *Shipping of Specimen(s)*

Frozen serum vials will be shipped from clinical sites to the CIML. Clinical sites will utilize a web-based specimen system (BSI-Web) to communicate with the CIML. The CIML will coordinate shipments of serum to the Fred Hutch Shared Resource facility or other collaborator, as needed.

9.2.3.4 *Site(s) Performing Correlative Study*

Assays will be performed at the Fred Hutch Shared Resource facility or other agreed upon collaborator or vendor.

9.2.4 *Kynurenine and tryptophan (Kyn/Trp) Ratios and Plasma Arginine levels – Exploratory Laboratory Correlative Study #4*

9.2.4.1 *Collection of Specimen(s)*

Blood draws will be performed by venipuncture on study subjects at time points before, during, and after treatment.

9.2.4.2 *Handling of Specimens(s)*

Plasma will be isolated by the local laboratory and frozen at -80°C.

9.2.4.3 *Shipping of Specimen(s)*

Plasma samples will be batch shipped overnight on dry ice to the CIML. Sites will utilize a web-based specimen system (BSI-Web) to communicate with the CIML. The CIML will coordinate the shipment of samples to the agreed upon collaborator or vendor.

9.2.4.4 *Site(s) Performing Correlative Study*

Kynurenine and tryptophan and Arginine levels will be assessed at an agreed upon collaborator or vendor to be determined.

